3.2.4. Incidence of adverse events, safety laboratory tests, vital signs and ECG abnormalities

3.2.4.1. Adverse Events

An adverse event (AE) is considered a Treatment Emergent Adverse Event (TEAE), relative to a given treatment, if the event starts during the effective duration of treatment, i.e. starting on, or after, the date and time of the first dose, but before the end of Part A (i.e. Week 12 for participants continuing to Part B; or follow-up contact [28-35 days after last dose], for those participants not continuing to Part B of the study).

A Treatment-Emergent Serious Adverse Event (TESAE) is a TEAE which also meets the definition of a Serious Adverse Event (SAE)

A 3-tier approach will be used to summarize TEAEs. Under this approach, TEAEs are classified into 1 of 3 tiers: -

Tier 1 events: These are prespecified events of clinical importance and are maintained in a list in the product's Safety Review Plan (or similar, e.g. Safety Surveillance Review Plan). Appendix 2

Tier 2 events: These are events that are not tier 1 but are "common." A Medical Dictionary for Regulatory Activities (MedDRA) preferred term (PT) is defined as a Tier 2 event if there are at least 5% of participants reporting the event in any treatment group.

Tier 3 events: These are events that are neither Tier 1 nor Tier 2 events.

Potential immunogenic AEs will be medically evaluated and categorized as per guidances as: 1) Hypersensitivity, 2) Anaphylaxis, 3) Angioedema, 4) Delayed I-AE response and / or 5) Cytokine Release syndrome. See Appendix 2 for Sampson Criteria.

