#### 4. STUDY DESIGN

#### 4.1. Overall Design

This is a Phase 2, randomized, double blind, placebo-controlled study of the efficacy, safety, and tolerability of three different doses of ponsegromab compared to matching placebo in patients with NSCLC, CRC, or PANC, receiving standard of care (which may include

systemic therapy), who have elevated levels of GDF-15 and cachexia. The double-blind period is followed by an optional open-label extension period.

The Screening visit will occur no more than 28 days and no less than 7 days, prior to Randomization. The 7-day minimum duration between Screening and Randomization visits will ensure that the GDF-15 results are available to inform the investigator's assessment of eligibility and the 7-day collection of PRO and physical activity data. Following the Screening period to confirm eligibility, approximately 168 study participants, who meet the entry criteria, will be randomized to study intervention (one of 3 dose groups of ponsegromab or matching placebo) and will be stratified by treatment with or without platinum-based chemotherapy (see Appendix 12), which is known to induce GDF-15 and therefore may impact the response to ponsegromab treatment. The 12-week double-blind dosing period (Part A) will consist of a total of 3 doses administered Q4W SC.

A PK substudy will be conducted in approximately 36 of the approximately 168 participants (approximately 9 in each treatment group in Part A). Up to 3 additional PK and PD samples (two samples during Part A and one sample during Part B, if relevant), will be collected in these participants at timepoints during the study outlined in Sections 1.2 schema and 1.3 SoA.

On completion of Part A, participants will have the opportunity to enter an optional OLT period (Part B) consisting of ponsegromab 400 mg Q4W SC for up to 1 year. The investigator and participant must decide at the Week 8 visit if they wish to continue to the optional OLT period.

Participants opting to continue to the OLT period will receive their first dose of open-label ponsegromab 400 mg at the Week 12 visit, which is the last visit of the double-blind portion. Upon completion of the OLT period, there will be a follow-up visit (Week 72) which is to occur 56 to 63 days post last dose of study intervention.

Participants who do not proceed with the optional OLT period are to complete the Week 12 visit and a follow-up visit at Week 16.

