2.3. Study Design

This is a Phase 2, randomized, double-blind, placebo-controlled study of the efficacy, safety, and tolerability of three different doses of ponsegromab compared to matching placebo in patients with NSCLC, CRC, or PANC, receiving standard of care (which may include systemic therapy), who have elevated levels of GDF-15 and cachexia. The double-blind period is followed by an optional open-label extension period.

Following the Screening period to confirm eligibility, approximately 168 study participants, who meet the entry criteria, will be randomized to study intervention (one of 3 dose groups of ponsegromab or matching placebo) and will be stratified by treatment with or without platinum-based chemotherapy, which is known to induce GDF-15 and therefore may impact the response to ponsegromab treatment. The 12-week double-blind dosing period (Part A) will consist of a total of 3 doses administered Q4W SC.

A PK substudy will be conducted in approximately 36 of the approximately 168 participants (approximately 9 in each treatment group in Part A). Up to 3 additional PK and PD samples (two samples during Part A and one sample during Part B, if relevant), will be collected in these participants.

On completion of Part A, participants will have the opportunity to enter an optional OLT period (Part B) consisting of ponsegromab 400 mg Q4W SC for up to 1 year. The investigator and participant must decide at the Week 8 visit if they wish to continue to the optional OLT period. Participants who do not proceed with the optional OLT period are to complete the Week 12 visit and a follow-up visit at Week 16.

Figure 1 lays out the structure of the study, including follow-up, for all participants depending on whether they enter the optional OLT period.

[figure not shown]
[figure not shown]

Figure 1. Study Design

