3.2.2. Change from baseline in FAACT sub-scale scores at Week-12

- FAACT-ACS
- FAACT-5IASS

The FAACT combines the FACT-G core instrument and ACS. FACT-G is a summated score of 27 items pertaining to physical well-being (7 items), emotional well-being (6 items), functional well-being (7 items), and social well being (7 items) in the past 7 days. Each of the items uses a 5-point (0 to 4) scale. ACS is a 12 item summated scale containing items specific to patients' perceptions of appetite and weight, also using the 5 point scale. Adding the 12 ACS items to the FACT-G produces the 39 item FAACT. Higher scores are associated with a higher health-related quality of life.

See Appendix 1 for FAACT scoring guidelines showing the calculation of FAACT subscales and total scores (including FAACT-ACS and -5IASS).

Change from baseline will be calculated at all post-baseline timepoints.

3.2.3. Change from baseline score for the questions from the Cancer Related Cachexia Symptom Diary (CRCSD) at Week 12 related to:

- Anorexia/appetite
- Nausea;
- Vomiting;
- Fatigue

The CRCSD is a daily (evening), self-reported questionnaire that measures severity of symptoms related to cancer cachexia: appetite, nausea, vomiting, and fatigue. The measure consists of 4 questions that ask study participants to rate the severity of their symptoms over the past 24 hours on an 11 point NRS, apart from Vomiting which is measured on a numerical value from 0 to 30.

Weekly averages (on Day 1 and at Weeks 4, 8 and 12) will each be calculated as the mean taken over the 7 days immediately prior (e.g. if the Week 4 visit occurs on Day 29, the Week 4 average will be taken over Days 22 to 28; if the Week 8 visit occurs on Day 57, the Week 8 average will be taken over Days 50 to 56; and if the Week 12 visit occurs on Day 85, the Week 12 average will be taken over Days 78 to 84). If fewer than 4 days of scores are recorded, the mean should be treated as missing.

Baseline is defined as the mean taken over the 7 days prior to Day 1 (e.g. Days -7 to -1). Change from baseline will be calculated for all post-baseline weekly averages.

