3.4.12. Survival status at end of Part A

The survival status at the end of Part A will be recorded for each participant. End of Part A is considered Week 12 for all participants (regardless of whether they enter the optional Part B or not).

The time (days) to death during Part A (up to Week 12) will also be calculated for each participant.

3.4.13. Response as defined by a ≥3.5% increase from baseline in body weight at Week 12

Additionally, response, as defined by a ≥3.5% increase from baseline in body weight at Week 12, will be defined as having two levels: 'Response' and 'Non-response'. The former will be based on participants having a ≥3.5% increase from baseline in body weight at Week 12. Otherwise, participants will be classed as having a 'Non-response'. Participants with an intercurrent event of premature discontinuation of study intervention, prohibited procedure/medication or inadequate compliance prior to Week 12 will have their Week 12 value censored (if not missing). Missing or censored values at Week 12 will be imputed as described in Section 5.3.1. Participants who die during the study will be classed as having a 'Non-response' after imputation. This endpoint will be calculated similarly for Week 4 and Week 8.

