6.2.4.1. Adverse Events

Adverse events (Tier 1, 2 and 3 AEs as described in Section 3.2.4.1) will be summarized by treatment group (including ponsegromab combined) and overall, in accordance with sponsor reporting standards. The adverse events will be sorted in descending frequency within a system organ class. If applicable, subject discontinuations due to adverse events will be detailed and summarized.

Incidence and severity of TEAE and TESAE tables will additionally be produced ('All causality' and 'Treatment related', separately) to summarise the total number of adverse events by preferred term, which will be reported by treatment group (including ponsegromab combined) and overall.

TEAEs classed as Tier 2 events will each be tabulated by treatment group (including ponsegromab combined). The number and percentage of participants will be presented, along with the risk difference (and 95% confidence interval) between each dose of ponsegromab and placebo. No adjustment for multiplicity will be used.

Tier 2 TEAEs will also be presented graphically in two-panel plots; the left panel will present the proportions of TEAEs observed in a dose group of (including ponsegromab combined) and separately placebo, while the right panel will display the 95% confidence interval for the risk differences for each TEAE. A vertical line corresponding to the value of 0 will be added to the right-hand plot. Each panel will be paged by dose of ponsegromab.

Tier 2 TEAE outputs will be ordered in descending point estimate of risk difference within System Organ Class. If two or more events have the same frequency, they will be sorted alphabetically by preferred term. Footnotes will be included on the tables to provide proper interpretation of confidence intervals and to describe how the comparison was conducted, e.g. "Confidence intervals are not adjusted for multiplicity and should be used for screening purposes only. 95% Confidence intervals are provided to help gauge the precision of the estimates for Risk Difference. Risk Difference is computed as ponsegromab versus placebo."

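### The Part A TEAE window closes at a different time depending on Part B entry, and the planned between-arm risk differences do not allow for it

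*SAP*

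**What the plan says.** SAP 3.2.4.1 opens the treatment-emergent window at the first dose and sets its close as follows: "before the end of Part A (i.e. Week 12 for participants continuing to Part B; or follow-up contact". The second closing date is for anyone who stays out of Part B, and a bracket in the same sentence places that contact 28 to 35 days from the final dose. Protocol 9.3.1 and SAP 2 have the same structure, in that Part A reporting includes follow-up only for participants who do not go on to Part B. SAP 3 excludes safety data collected after the Week 12 dose for those who do.

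Entry to Part B is a decision, not a design feature. Protocol 4.1: "The investigator and participant must decide at the Week 8 visit if they wish to continue to the optional OLT period".

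SAP 6.2.4.1 then tabulates the number and percentage of participants with each Tier 2 event, "along with the risk difference (and 95% confidence interval) between each dose of ponsegromab and placebo". The stated analyses contain no exposure-adjusted rate and no common cut-off.

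For survival the same SAP uses one date. Section 3.4.12: "End of Part A is considered Week 12 for all participants (regardless of whether they enter the optional Part B or not".

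**The concern.** A crude percentage compares arms fairly only if the arms are observed for comparable times. Here the closing date depends on something that happens after randomisation and may reflect how the participant is doing. Part B is open-label ponsegromab 400 mg, and participants can notice changes in their own weight and appetite even under the blind. If entry differs by arm, one arm accumulates more time after Week 12, and that time comes only from participants who declined. Part of the risk difference would then reflect uptake rather than treatment.

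Tier 2 status could also shift. A term qualifies when at least 5% of participants in any one group report it. At 42 per arm that is 3 participants (0.05 × 42 = 2.1, rounded up), so a few follow-up events in one arm can decide which terms are compared.

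The SAP also ends up with two definitions of the end of Part A, one for deaths and one for adverse events.

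**Working it through.** **Inputs (nominal days)**
- Doses: SAP 2.3, "The 12-week double-blind dosing period (Part A) will consist of a total of 3 doses administered Q4W SC", so Day 1, Week 4 (Day 29) and Week 8.
- Last Part A dose: SAP 3.2.3, in its diary-averaging example, "if the Week 8 visit occurs on Day 57". The same example puts Week 12 on Day 85.
- Follow-up for those not continuing: Week 16, Day 113 with a window of +7 days (Protocol Table 1, SAP 2.3).
- Randomised per arm: 42 (Protocol 9.5).
- Part B uptake by arm and event risks: not in the documents, so assumed and shown as ranges.

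**1. The plan's own figure.** The SAP places the follow-up contact 28-35 days after the last dose. From the schedule, 113 − 57 = 56 and 120 − 57 = 63 days, so the figure does not reproduce. It does match the interval from the Week 12 visit: 113 − 85 = 28 and 120 − 85 = 35 days.

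**2. Extra observation after Week 12, all three doses given**
- Bracket as written: the window closes on Day 57 + 28 = 85 to 57 + 35 = 92, which is 0-7 days beyond Week 12 (0-8% of 84 days).
- Week 16 visit: the window closes on Day 113-120, which is 28-35 days beyond Week 12 (33-42% of 84 days).

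**3. Early stoppers on the bracket reading.** After dose 1 only, the window closes on Day 29-36. After dose 2, it closes on Day 57-64. Both fall before Week 12, so not entering Part B does not always mean longer observation.

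**4. Spurious risk difference with no true effect.** Let r be the risk by Week 12, e the extra days and d the gap between arms in the share observed beyond Week 12. With a constant hazard, the risk over 84 + e days is 1 − (1 − r)^((84 + e)/84), and

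spurious difference = d × [1 − (1 − r)^((84 + e)/84) − r].

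For r = 20% the risk becomes 21.5% at e = 7, 25.7% at e = 28 and 27.1% at e = 35. With d = 30 points, in percentage points:

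| Risk by Week 12 | e = 0 | e = 7 | e = 28 | e = 35 |
|---|---|---|---|---|
| 10% | 0 | 0.24 | 0.93 | 1.16 |
| 20% | 0 | 0.44 | 1.72 | 2.13 |
| 40% | 0 | 0.75 | 2.82 | 3.45 |
| 60% | 0 | 0.88 | 3.16 | 3.81 |

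The result is proportional to d. A 10-point gap gives one third of these values, and equal uptake gives zero.

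**5. If the hazard rises after Week 12.** For illustration, tripling it in non-enterers for 28 days equals 84 further days at the original hazard. The risk is then 1 − 0.8² = 36%, and the spurious difference is 0.30 × (36 − 20) = 4.8 points. Nothing in the documents supports a particular rise.

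**6. Precision.** At r = 20% and 42 per arm, the 95% half-width is 1.96 × √(2 × 0.2 × 0.8/42) = 0.171, or about 17 points.

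**7. With a common Week 12 cut.** Here e = 0 for everyone, and the spurious difference from Part B entry is 0 at any uptake gap.

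**The case against.** The case for leaving the plan alone has real weight.

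- **Size.** The SAP's own bracket makes the windows nearly equal for anyone given all three doses. Even on the Week 16 reading the effect is small beside a 17-point half-width. This stands.
- **Uptake.** Part B is open to all arms and the decision is made under the blind. With equal uptake, participants given all three doses have the same mean window in each arm. This stands: unequal uptake is a condition, not a documented fact.
- **Status.** SAP 6.2.4.1 requires a footnote limiting the intervals to screening use and calls safety analysis exploratory. SAP 5.1 does not list safety among the tested endpoints. This stands and limits the consequence.
- **Deliberate design.** Entrants must be cut before open-label dosing, and follow-up captures late events for an antibody whose total half-life reached 30.9 days at 300 mg (Protocol 2.2.1.3). This justifies collecting and reporting late events. It does not justify mixing them into a between-arm comparison for some participants only.
- **Sponsor reporting standards** may supply further summaries. They are not in the documents, so this cannot be credited or ruled out.

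A reader might also infer something stronger: that placebo participants will decline Part B more often, be observed longer while sicker, and so make ponsegromab look safer than it is. The documents do not support that. They give no uptake by arm. Participants who die or withdraw before Week 12 add no later time on either reading, and on the bracket reading early stoppers are observed for less time. The direction could be either way.

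**Conclusion.** The point holds in a limited form. The Part A window for treatment-emergent events depends on a post-randomisation choice, and the stated risk differences do not adjust for it. Whether this biases anything depends on Part B entry differing by arm, which is unknown, as is the direction. It would be wrong to say that non-enterers are observed a third longer as a settled fact, or that the safety comparison is confounded. The first needs the Week 16 reading and the second needs unequal uptake.

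Under an assumed 30-point gap, 20% risk and constant hazard, the range is 0 to about 0.4 points (bracket) or about 1.7 to 2.1 points (Week 16). A higher event risk enlarges it, as would a hazard that rises after Week 12. The disagreement between the bracket and the Week 16 schedule is an error in its own right and needs correcting whatever the uptake. Overall this is a cheap improvement, not a threat to the trial's conclusions.

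**What to change.** 1. In SAP 3.2.4.1 and 6.2.4.1, define the window for the between-arm Part A TEAE and TESAE tables, and for the Tier 2 risk differences and plots, as first dose to Week 12 and before any open-label dose. Apply it to every participant, including those who stop treatment early but remain in the study. This matches SAP 3.4.12.
2. Report events after Week 12 in participants who do not enter Part B in a separate follow-up table.
3. Reconcile the bracket of 28-35 days after last dose with the Week 16 visit at Day 113 to 120, so that the follow-up contact has one definition.

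The cost is SAP wording and a date cut in the programs, with no new data. The downside is that late events in non-enterers leave the main between-arm comparison, though they are still reported. The cut removes the dependence on Part B entry only. Participants who leave the study before Week 12 still contribute less time, as they would in any crude incidence table.

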## **Overall Design:**

This is a Phase 2, randomized, double-blind, placebo-controlled study of the efficacy, safety, and tolerability of three different doses of ponsegromab compared to placebo, administered for 12 weeks, in patients with NSCLC, PANC, or CRC who have elevated concentrations of GDF-15 and cachexia. The double-blind period is followed by an optional open-label (Part B) extension period.

The Screening visit will occur no more than 28 days and no less than 7 days, prior to Randomization. The 7-day minimum duration between Screening and Randomization visits will ensure that the GDF-15 results are available to inform the investigator's assessment of eligibility and the 7-day collection of PRO and physical activity data. Following the Screening period to confirm eligibility, approximately 168 study participants, who meet the entry criteria, will be randomized to study intervention (one of 3 dose groups of ponsegromab or matching placebo) and will be stratified by treatment with or without platinum-based chemotherapy, which is known to induce GDF-15 and therefore may impact the response to ponsegromab treatment. The 12-week double-blind dosing period (Part A) will consist of a total of 3 doses administered Q4W SC.

A PK substudy will be conducted in approximately 36 of the approximately 168 participants (approximately 9 in each treatment group in Part A). Up to 3 additional PK and PD samples (two samples during Part A and one sample during Part B, if relevant), will be collected in these participants at timepoints during the study outlined in Sections 1.2 schema and 1.3 SoA.

On completion of Part A, participants will have the opportunity to enter an optional OLT period (Part B) consisting of ponsegromab 400 mg Q4W SC for up to 1 year. The investigator and participant must decide at the Week 8 visit if they wish to continue to the optional OLT period.

Participants opting to continue to the optional OLT period will receive their first dose of open-label ponsegromab 400 mg at the Week 12 visit, which is the last visit of the double-blind portion. Upon completion of the optional OLT period, there will be a follow-up visit (Week 72) which is to occur 56 to 63 days post last dose of study intervention.

Participants who do not proceed with the optional OLT period are to complete the Week 12 visit and a follow-up visit at Week 16.

Additional follow-up may be conducted for safety evaluation, at the discretion of the investigator.

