## 1.2. Schema

#### 1.3. Schedule of Activities

The SoA table provides an overview of the protocol visits and procedures. Refer to the section of the protocol for detailed information on each procedure and assessment required for compliance with the protocol.

The investigator may schedule visits (unplanned visits) in addition to those listed in the SoA table, to conduct evaluations or assessments required to protect the well-being of the participant.

Table 1.	Schedule of Activities for Part A Double-Blind
----------	--

Visit Identifier	Screening				]	Part A: D	ouble-Bl	ind a		F/U Part A	ED Part A
Abbreviations used in this table may be found in											
Appendix 13											
Week #			4	5 b,c	8 d	9 c,e (PK substudy only)	10 c,f	11 c,e (PK substudy only)	12	16	
Day -relative to start of study intervention (Day 1)	-28 to -7	1	29	36	57	64	71	78	85	113	
Visit Window (Days)			±3	-3/+7	±3	±2	±7/±3 f	±2	±2	+7	
Informed consent	X										
Review eligibility criteria	Х	Х									
Medical History and Physical Examination											
Medical history	X										
Demography	X										
Full Physical examination (+ Height at Screening only) g	X								Х		Х
Abbreviated Physical examination g			Х		Х						
Vital signs	X		Х		Х				Х		Х
12-Lead ECG	Х				Х				Х		Х
ECOG PS	X								Х		Х
Contraception check	Х	Х	Х		Х				Х	Х	Х
Laboratory Assessments											
Hematology	X				Х				Х		Х
Blood chemistry	X				Х				Х		Х
Pregnancy test h	Х	Х	Х		Х				Х	Х	Х
Blood sample for GDF-15 (Roche Assay)	X										
Blood sample for GDF-15 (Pfizer Assay(s)) i	X	Х	X	Х	Х	Х	X	Х	Х	Х	Х
Blood sample for ponsegromab PK i		Х	Х	Х	Х	Х	X	Х	Х	Х	Х

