#### Table 1. Schedule of Activities for Part A Double-Blind

Visit Identifier	Screening				F	F/U Part A	ED Part A				
Abbreviations used in this table may be found in											
Appendix 13											
Week #			4	5 b,c	8 d	9 c,e (PK	10 c,f	11 c,e (PK	12	16	
						substudy		substudy			
Day -relative to start of study intervention (Day 1)		1	29	36	57	64	71	78	85	113	
	-28 to -7										
Visit Window (Days)			±3	-3/+7	±3	±2	$\pm 7/\pm 3^{f}$	±2	±2	+7	
Retained research samples for biomarkers (Prep B 1.5 &		Х							Х		Х
Prep B 2.5) r											

a. All participants, regardless of proceeding with the optional OLT period (Part B), will complete the Week 12 visit. Participants proceeding with the optional OLT period (Part B) will complete all Week 12 study procedures before receiving the first dose of OLT study intervention. Transportation to and from the study site may be provided for study participants for Part A visits, as permitted by the country, study site, and participant.

b. The Week 5 visit is considered an optional visit to collect PK and GDF-15 samples as well as measurement of weight and SAE/AE monitoring based upon participant availability. It will not be considered a protocol deviation if the participant is unable to make this visit.

c. The PK and PD assessments at Week 5 and 10, as well as Week 9 and 11 in PK sub-study only may be conducted at participant's home or current residence if it is feasible to be performed by the site for flexibility of participant.

- d. The investigator and participant must decide at the Week 8 visit if they wish to continue to the optional OLT (Part B).
- e. Visits at Weeks 9 and 11 are only applicable for participants enrolled in PK sub-study.
- f. For participants in PK substudy, visit window for Week 10 is ±3 days
- g. All physical exams (full and abbreviated) will include an assessment for ascites and/or edema. In addition, ascites and/or edema will be captured as an AE on the AE CRF. See Section 8.3.1.

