#### 4.4. End of Study Definition

The end of the study is defined as the date of the last visit of the last participant in the study globally.

A participant is considered to have completed the study if they have either completed Part A (including follow-up), or has completed Part A and has entered, and completed, the OLT extension Part B, as described in the SoA.

The PCD is the date of the last visit for Part A (Week 12,) for the last participant.

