Participants will undergo review of concomitant treatments, vital signs, and assessment for resolution of any treatment-related AEs through approximately 56 days following discontinuation of study intervention. Participants continuing to experience AEs at this point following discontinuation of treatment will continue to be followed at least every 4 weeks until resolution or determination, in the clinical judgment of the investigator, that no further improvement is expected. If the unresolved AE is considered by the investigator as possibly related to or associated with ADA formation, the participant will be asked to return for drug concentration and ADA blood sampling at up to 3-month intervals, until the last follow-up of the AE.

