#### 9.3.1. General Considerations

Part A and Part B of the study will be presented separately. For objectives relating to Part A of the study, each treatment arm will be reported separately through the 12-week double-blind treatment period only (including follow-up for any participants not continuing onto Part B of the study).

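### SAP 3.2.4.1 dates the Part A follow-up contact that closes the TEAE window at 28–35 days after last dose, but by the protocol's schedule it is nominally 56–63 days

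*SAP*

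**What the plan says.** SAP 3.2.4.1 counts an adverse event as treatment-emergent if it starts on or after the first dose and before the end of Part A. The end of Part A is then defined in two ways. For participants continuing to Part B it is Week 12. For the others it is "follow-up contact [28-35 days after last dose], for those participants not continuing to Part B of the study".

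The protocol supplies the dates. The synopsis says that Part A "will consist of a total of 3 doses administered Q4W SC". Table 1 of Protocol 1.3 places those doses at Day 1, Week 4 (Day 29) and Week 8 (Day 57, ±3). Week 12 (Day 85, ±2) also carries a dosing mark, but footnote a ties it to Part B: participants going on "will complete all Week 12 study procedures before receiving the first dose of OLT study intervention". Participants who do not go on attend Week 12 and then a follow-up visit at Week 16 (Day 113, +7); SAP 2.3 repeats this.

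Protocol 9.3.1 reports Part A through the double-blind period, "including follow-up for any participants not continuing onto Part B of the study". Protocol 4.4 and SAP Section 2 likewise count that follow-up as part of Part A. Protocol 8.4.1 has adverse events actively collected at least through the final planned follow-up visit.

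**The concern.** The definition names an event (the follow-up contact) and attaches a day count to it, and the two do not describe the same date. This sentence is the operative rule for the TEAE and TESAE labels. Those labels drive the incidence and severity tables in SAP 6.2.4.1 and the Tier 2 risk differences versus placebo. A programmer and a QC programmer could each follow the sentence and arrive at different end dates for the same participant. Under the day count, events from the last weeks before Week 16 would be in the database but not in those tables.

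**Working it through.** **Inputs** (Protocol 1.3, Table 1, in days relative to the start of study intervention): doses on Days 1, 29 and 57; Week 8 window ±3 (Days 54–60); Week 12 on Day 85, window ±2 (Days 83–87); Week 16 follow-up on Day 113, window +7 (Days 113–120).

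**1. Which starting point gives the SAP's figure?** Interval = follow-up day (113 to 120) minus starting day.

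| Starting point | Nominal interval | With visit window |
|---|---|---|
| Day 1 dose | 113−1 = 112 to 120−1 = 119 | not applicable |
| Week 4 dose, Day 29 | 113−29 = 84 to 120−29 = 91 | 113−32 = 81 to 120−26 = 94 |
| Week 8 dose, Day 57 (last Part A dose) | 113−57 = 56 to 120−57 = 63 | 113−60 = 53 to 120−54 = 66 |
| Week 12 visit, Day 85 | 113−85 = 28 to 120−85 = 35 | 113−87 = 26 to 120−83 = 37 |

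Only the Week 12 visit reproduces 28–35, and the only dose given then is the first open-label dose, to participants whom this clause excludes. That the bracket was counted from Week 12 is an inference; that it does not fit the last dose is arithmetic. For anyone dosed and followed up within the windows, the shortest possible interval (53 days) exceeds the longest that the SAP allows (35 days).

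**2. Where would the day count close the window?** From a Day 57 dose, 57+28 = Day 85 and 57+35 = Day 92.

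**3. How far is that from the follow-up contact?**
- If 28 days were programmed: 113−85 = 28 to 120−85 = 35 days.
- If 35 days were programmed: 113−92 = 21 to 120−92 = 28 days.
- Overall: nominally 21–35 days. With the Week 8 window: 53−35 = 18 to 66−28 = 38 days.

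**4. Parallel in Part B.** The last dose at Week 64 is Day 449 and the follow-up at Week 72 is Day 505 (+7): 505−449 = 56 and 512−449 = 63. The synopsis describes this correctly: "there will be a follow-up visit (Week 72) which is to occur 56 to 63 days post last dose of study intervention". The layout is the same, but it shows only how such an interval is counted. Part B has its own supplemental SAP and does not govern Part A.

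**The case against.** The strongest reply is that the rule is already clear. The sentence ends the window at a named contact, other sections identify that contact as Week 16, and the bracket is only a gloss. A range cannot be programmed as a cut-off unless someone picks a number. A 28-day cut would also close the window at Day 85 for non-continuers, the same nominal day as Week 12 for continuers, and so defeat the distinction that the sentence draws. All of this stands. The named contact is the natural reading, and under it nothing is lost.

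It does not rescue the bracket, which is wrong even as a description for every participant dosed and followed up on schedule. The SAP does use a count from last dose as a rule elsewhere: Section 4 dates discontinuation of study intervention at last dose plus 29 days. SAP 3.4.12 also sets the end of Part A at Week 12 for everyone, though only for survival status. A single explicit end point for TEAEs is therefore worth stating.

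A reader might infer two stronger points that the documents do not support:

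- *That the safety tables will omit events.* They will only if the day count is used, and the SAP does not say that it will be. How the sponsor's reporting standards derive the label cannot be seen from these documents.
- *That Protocol 7.1 confirms 56 days from last dose.* It provides for "assessment for resolution of any treatment-related AEs through approximately 56 days following discontinuation of study intervention". That count runs from discontinuation, which the SAP dates at last dose plus 29 days, so it would reach about 29+56 = 85 days after last dose. It also concerns resolution of treatment-related events, not the onset of new ones.

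**Conclusion.** The interval stated in SAP 3.2.4.1 is wrong as written. The contact it describes is nominally 56–63 days after the last Part A dose (53–66 with the Week 8 window), not 28–35. This is an internal inconsistency in a safety analysis definition, and it should be corrected before the TEAE label is programmed.

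The consequence depends on the implementation. With the actual contact date the loss is zero. With the day count, the window closes nominally 21–35 days early (18–38 with the Week 8 window) for non-continuers dosed at Week 8 and still being followed. Events starting in that gap would drop out of the TEAE and TESAE tables and the Tier 2 risk differences. The documents give neither the number of such participants nor their event rates, so the number of events cannot be computed.

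The figures assume a last dose at Week 8 and a follow-up contact at Week 16, both within their windows. They do not cover doses given outside the window with sponsor agreement (Protocol 6.5), or participants whose last dose was earlier. Efficacy analyses, sample size and adverse event collection are not affected.

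**What to change.** Amend SAP 3.2.4.1 as follows:

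- For participants not continuing to Part B, end the TEAE window at the date of the actual Part A follow-up contact (Week 16).
- Delete the bracketed day count, or replace it with a note, marked as nominal only, that the contact falls about 56–63 days after the Week 8 dose. It should not act as the rule: someone last dosed on Day 29 or Day 1 who attends Week 16 is nominally 84–91 or 112–119 days from last dose.
- State that, for non-continuers with no such contact (death, withdrawal, loss to follow-up), the window ends at the end of their Part A participation, meaning the last date on which adverse events were collected. Protocol 9.5 assumes about 30% discontinuation, so this case will need a rule.

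The cost is a few lines of SAP text. No new data and no new outputs are needed.
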